## **STUDY PROTOCOL AND STATISTICAL ANALYSIS PLAN**

### **1. Title of the Study**

Impact of Using a Mirror in the Second Stage of Labor on Childbirth Duration and Experience:  
A Randomized Controlled Trial

### **2. Background and Rationale**

Childbirth is a critical period for maternal health. The second stage of labor, from full cervical dilation to birth, is particularly demanding. Recent studies suggest that visual biofeedback (e.g., using a labor mirror) may improve maternal control, reduce fear, and shorten labor. However, there is limited empirical evidence from randomized controlled trials, especially in the Turkish context.

### **3. Study Objectives and Hypotheses**

#### **Aims:**

- To assess the impact of labor mirror use on the duration of the second stage of labor.
- To evaluate the effect of labor mirror use on maternal birth experience.

#### **Hypotheses:**

**H0-1:** There is no difference in second-stage labor duration between the mirror and control groups.

**H1-1:** There is a significant difference in second-stage labor duration between the groups.

**H0-2:** There is no difference in Childbirth Experience Questionnaire (CEQ) scores between the mirror and control groups.

**H1-2:** There is a significant difference in CEQ scores between the groups.

### **4. Study Design**

Randomized controlled, non-blinded, parallel-group design.

### **5. Study Setting and Timeline**

**Site:** Kocaeli Darica Farabi Training and Research Hospital, Turkey

**Study Period:** February 2023 – July 2024

## 6. Participants

### **Inclusion Criteria:**

- Aged  $\geq 18$  years
- Gestational week 38–42
- Low-risk, healthy singleton pregnancy
- Literate in Turkish

### **Exclusion Criteria:**

- Preterm labor, epidural, fetal complications, meconium-stained fluid
- Assisted deliveries (e.g., forceps, vacuum)
- Withdrawal from mirror use or complications in second stage

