## 7. Sample Size and Randomization

Using G\*Power (v3.1.9.2) based on Palompon et al. (2011), effect size=1.93, power=0.99,  $\alpha=0.05$ :

Total: 122 participants (61 per group)

Random Allocation Software was used.

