## 8. Interventions

**Intervention Group:** Participants were informed and consented. A perineal mirror was fixed to the delivery bed during the second stage of labor, allowing women to visualize fetal descent.

**Control Group:** Received standard care with no mirror.

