## **11. Statistical Analysis Plan**

Descriptive statistics (mean, SD, frequencies)

Shapiro-Wilk test for normality

Mann-Whitney U test for group comparisons

Pearson Chi-Square for categorical variables

p-value <0.05 considered statistically significant

Software: IBM SPSS Statistics v20

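### Withdrawal from the mirror is an exclusion that, read naturally, arises only after allocation and only in the mirror arm, and Section 11 names no as-randomised analysis

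*Combined protocol and SAP*

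**What the plan says.** All references are to the combined protocol and SAP.

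- Section 6, Exclusion Criteria, lists "Withdrawal from mirror use or complications in second stage". It also lists assisted delivery.
- Section 8 describes the intervention group thus: "A perineal mirror was fixed to the delivery bed during the second stage of labor". Of the controls it says: "Received standard care with no mirror". It also says of the intervention group "Participants were informed and consented", without giving the order of consent and allocation.
- Section 7 plans 61 women per group and names the randomisation software, but not when allocation takes place.
- Section 11 gives "Mann-Whitney U test for group comparisons" and a 0.05 threshold. It names no analysis population and no handling of withdrawn or excluded women, and no other section does so.

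**The concern.** A control woman has no mirror to withdraw from. The criterion therefore filters one arm only, on an event that takes place while the primary outcome is being generated. The trial is not blinded (Section 4), so a woman decides whether to continue knowing that she has the mirror. It is plausible, though the documents do not show it, that this decision depends on how long labour is taking or how it feels. Those are the primary and secondary outcomes.

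If so, H1-1 and H1-2 would be tested between selected mirror users and unselected controls, and randomisation would no longer protect either comparison.

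Assisted delivery and second-stage complications can remove women from either arm. They raise a related problem where they occur after allocation, but they are not confined to one arm.

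**Working it through.** **Plan figures.** The plan gives no withdrawal rate and no duration distribution, so it has no figure for this bias that could be reproduced. Only 61 per group, the 0.05 threshold and the effect size of 1.93 come from the documents; every other input below is an assumption. The stated sample size does not follow from its stated inputs: 2 × (1.960 + 2.326)² / 1.93² = 9.9, or 10 per group (11 with the t distribution), against 61. That is a separate matter, and nothing here depends on it.

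**1. Shift from a one-arm exclusion.** If a fraction w of the mirror arm is dropped and their mean lies k SD above the arm mean, the mean of those who remain moves by −w·k/(1 − w).
- w = 0.05, k = 0.5: −0.03 SD
- w = 0.10, k = 0.5: −0.06 SD
- w = 0.20, k = 1: −0.25 SD

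The sign reverses if withdrawers lie below the arm mean. With k = 0 there is no shift.

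**2. Rank-only worst case.** Take two identical sets of 61 values (as-randomised p = 1.00) and drop the k most extreme values from one set. The Mann-Whitney statistic then departs from its null mean by k(61 − k)/2. Its variance is about (61 − k) × 61 × (123 − k)/12, before a small tie correction. With continuity correction:
- k = 6 (9.8%): 164.5 / 180.8 = 0.91, p = 0.36
- k = 13 (21.3%): 311.5 / 163.8 = 1.90, p = 0.057
- k = 14 (23.0%): 328.5 / 161.4 = 2.04, p = 0.042

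**3. Results near the threshold** (assumed shifted normal quantiles). From p = 0.10, dropping the 2 longest mirror-arm durations (3.3%) gives p = 0.047. From p = 0.20, dropping the 5 longest (8.2%) gives p = 0.037. In the other direction, from p = 0.04, dropping the 1 shortest gives p = 0.054.

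**4. Null simulation for duration.** Assumptions: lognormal with median 40 min and log-SD 0.7; log-odds of withdrawal changing by 0.5 to 1 per log-SD in either direction; removal from the mirror arm only; two-sided Mann-Whitney test; 20,000 replicates per scenario. Monte Carlo error is about 0.05 min and 0.15 to 0.25 percentage points.

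| Mirror arm removed | Mean shift, withdrawal rises with duration | Mean shift, withdrawal falls with duration | False positives |
|---|---|---|---|
| none | 0.1 min | 0.1 min | 4.9% |
| 5% | −1.0 to −2.2 min | +0.6 to +1.3 min | 5.1% to 5.7% |
| 10% | −2.0 to −4.0 min | +1.5 to +2.5 min | 5.6% to 7.4% |
| 20% | −3.8 to −7.2 min | +3.1 to +5.3 min | 7.5% to 14.4% |

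With withdrawal unrelated to duration, the shift is about 0 and false positives are 5.0% to 5.2% at every rate.

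**5. CEQ** (assumed normal, same selection model). Removing 10% shifts the mean by 0.05 to 0.09 SD, with 5.5% to 7.3% false positives. Removing 20% shifts it by 0.10 to 0.17 SD, with 7.4% to 14.0%.

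**6. A different selection model.** Here a normal outcome is correlated 0.3 to 0.6 with a latent tendency to withdraw (8,000 runs per scenario). False positives are 5.6% to 6.2% at 5% removed, 6.2% to 9.6% at 10%, and 7.8% to 18.0% at 20%. The pattern is the same, somewhat stronger at the upper end.

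**The case against.** The strongest reply is that the harm is conditional. The criterion sits in the participants section and does not say in terms that women leave the analysis. The timing of allocation is not given, and the word could cover women who declined the mirror at consent. Bias needs women to withdraw, after allocation, to be dropped, and to differ in outcome; the documents establish none of these. An unnamed analysis set in a short plan may be only a reporting gap.

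The numbers can also be read as modest. At 5% removed, the false-positive rate is close to nominal. The rank-only case needs perfectly selective removal of 14 of 61 women to cross 0.05, and the near-threshold examples were chosen to start close to it. The minute figures are means of a skewed assumed distribution: at the steepest slope the median shifts are about −1.1, −2.2 and −4.3 min at 5%, 10% and 20%. A large true effect would survive. At 0.78 SD, dropping the 15 shortest mirror-arm durations still leaves p = 0.029.

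Much of this stands. No bias is demonstrated, and every rate is assumed. But the consent-stage reading is the weaker one, since withdrawing from use implies that use was offered or begun and the same bullet concerns second-stage events. Survival of a large true effect does not answer the risk of a false positive when there is none. And a listed exclusion is a rule, not a silence: followed as written, it removes women from one arm.

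**Conclusion.** The concern holds and needs to be fixed. The plan states an exclusion that, on its natural reading, acts after allocation and in the mirror arm only, and nothing in Section 11 restores the comparison as randomised. Confidence in that is high.

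It does not extend to whether bias occurred, which way it went or how large it was. If no woman withdrew, this criterion changes nothing; if withdrawal was unrelated to outcome, the bias is essentially nil. Under the assumed duration model with outcome-related withdrawal, the effect on false positives is slight at 5% removal, moderate at 10%, and material at 20%. The case for change rests on the plan permitting a one-arm exclusion from its primary comparison, not on a demonstrated size of bias.

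**What to change.** **Section 6.** Keep as eligibility criteria only what is known before allocation, and state when allocation occurs. Do not use mirror withdrawal, or an assisted delivery or second-stage complication arising after allocation, to remove a woman from the analysis. If refusal before allocation was meant, say so.

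**Section 11.**
- Make the primary analyses of duration and CEQ include all randomised women with outcome data, in their allocated group.
- Measure duration from full dilation to birth, as Section 2 describes the second stage.
- State, with one rule for both arms, how women who never reach the second stage, or whose second stage ends in operative delivery, enter the Mann-Whitney comparison. The second rule is needed once assisted deliveries are no longer excluded.
- Report post-allocation exclusions, mirror withdrawals, missing outcomes and any replacements by arm, with reasons.
- Present mirror completers only as a labelled per-protocol sensitivity analysis.

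**Cost.** If the data exist, the cost is wording and a re-analysis. Section 10 lists the forms but not whether they were completed for excluded women. The study period to July 2024 and the past tense of Sections 7 and 8 suggest that conduct may be over. If outcomes were not collected, say so, give counts and reasons by arm, and limit the conclusion to mirror completers.

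The statistical price is dilution by non-adherence. Section 7 assumes "effect size=1.93, power=0.99". If withdrawers gain nothing, the effect falls to 1.93 × 0.90 = 1.74 at 10% withdrawal and 1.93 × 0.80 = 1.54 at 20%, and simulated power with 61 per group stays above 99%. At a smaller assumed effect of 0.5 SD, power would fall from 76% to about 67% and 56%.

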## 7. Sample Size and Randomization

Using G\*Power (v3.1.9.2) based on Palompon et al. (2011), effect size=1.93, power=0.99,  $\alpha=0.05$ :

Total: 122 participants (61 per group)

Random Allocation Software was used.

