### **Outcome Measures**

#### **Primary Outcome:**

Duration of second stage of labor (in minutes)

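### The stated sample-size inputs (effect size 1.93, power 0.99, alpha 0.05) do not produce 122 women; read as Cohen's d they need 22 to 26

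*Combined protocol and SAP*

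**What the plan says.** Section 7 (Sample Size and Randomization) names G*Power, cites an earlier study as the basis, lists "effect size=1.93, power=0.99" with alpha 0.05, and then gives the result: "Total: 122 participants (61 per group". It does not say what kind of effect size 1.93 is, which test was sized, whether the test is one- or two-sided, which endpoint was sized, or whether any allowance for losses was added.

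Other sections supply part of the context:

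- The primary outcome is "Duration of second stage of labor (in minutes".
- The first alternative hypothesis in section 3 has no direction: "There is a significant difference in second-stage labor duration between the groups". That implies a two-sided test.
- Section 11 plans the "Mann-Whitney U test for group comparisons".
- The exclusion criteria in section 6 include "Assisted deliveries (e.g., forceps, vacuum" and "Withdrawal from mirror use or complications in second stage". These can arise after allocation, so fewer than 61 per group may be analysed.

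No section gives a mean, an SD, a loss rate or another reason for 122.

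**The concern.** Section 7 reads as a calculation, with inputs followed by an output. A standardised difference of 1.93 is so large that about a dozen women per group would suffice even at 99% power. A result of 61 per group therefore signals that the effect size, the power or the number is misstated, or that the number was raised above the calculated minimum without saying so. The documents cannot show which.

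The trial is not underpowered for its stated effect. What is at stake is that this section is the only justification of the trial's size. A reader weighing a null result would take from it that the trial was built to detect 1.93 with 99% power, which does not describe what 61 per group can detect.

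**Working it through.** **Inputs.** From section 7: effect size 1.93, power 0.99, alpha 0.05, two equal groups, 61 per group. From section 3: a two-sided test. From section 11: Mann-Whitney. Assumption: 1.93 is Cohen's d.

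**Attempt to reproduce 122.** The normal approximation per group is

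n = 2 × (z₀.₉₇₅ + z₀.₉₉)² / d² = 2 × (1.960 + 2.326)² / 1.93² = 36.74 / 3.725 = 9.9, so 10 per group.

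The exact t-test calculation uses the noncentral t distribution with 2n − 2 degrees of freedom and noncentrality d × √(n/2). For Mann-Whitney, n is multiplied by the test's asymptotic efficiency relative to the t-test: 3/π for normal data, or 0.864, its minimum.

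| Test (two-sided 0.05) | Power one below | Smallest n per group | Power | Total |
|---|---|---|---|---|
| t-test | 0.983 (n = 10) | 11 | 0.9904 | 22 |
| Mann-Whitney, 3/π | 0.987 (n = 11) | 12 | 0.9926 | 24 |
| Mann-Whitney, 0.864 | 0.986 (n = 12) | 13 | 0.9916 | 26 |

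Simulation with normal data (20,000 replicates, Mann-Whitney) agrees: 98.6% at 11 per group and 99.1% at 12. The stated 122 is not reproduced. The ratio is 122/26 = 4.7 to 122/22 = 5.5.

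**Can another choice close the gap?**

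- One-sided tests need 10 to 11 per group.
- Two-sided alpha of 0.001 needs 20 (t-test) to 23 (Mann-Whitney, 0.864) per group.
- Inflation alone would imply a loss of 1 − 13/61 = 79% to 1 − 11/61 = 82%. Even 50% loss gives only 24/0.5 = 48 to 26/0.5 = 52 in total.
- Other meanings of 1.93, at alpha 0.05 and power 0.99: Cohen's f gives 8 in total, a hazard ratio 170 to 183 events, and an odds ratio converted to d (0.36) 562. A decimal slip gives 1,976 (d = 0.193) or 496 (f = 0.193).

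**Power at the stated size.** With 61 per group the noncentrality is 1.93 × √(61/2) = 10.66, and power is about 1.00.

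**What the trial can detect.** Smallest standardised difference at 80/90/99% power, Mann-Whitney, two-sided 0.05:

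| Analysed per group | Normal data (3/π) | Minimum efficiency (0.864) |
|---|---|---|
| 61 (all) | 0.52 / 0.61 / 0.80 | 0.55 / 0.64 / 0.84 |
| 55 (assumed 10% excluded) | 0.55 / 0.64 / 0.84 | 0.58 / 0.67 / 0.89 |
| 49 (assumed 20% excluded) | 0.59 / 0.68 / 0.90 | 0.62 / 0.71 / 0.94 |

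The exclusion rates are assumptions, since the documents give none. Simulation at 61 per group gave 79.4%, 90.2% and 99.0% power at d = 0.524, 0.606 and 0.801. Power at d = 0.5 is 72 to 76% with 61 per group and 62 to 67% with 49. Without an SD, none of this converts to minutes.

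**The case against.** The strongest reply is that the contradiction depends on reading 1.93 as Cohen's d, which section 7 does not say. One other reading fits: if 1.93 were a raw difference with an SD of 1.93/0.782 = 2.47, a two-sided t-test would need 61 per group for 99% power. But no SD appears anywhere, and the text calls 1.93 an effect size. If that is what was done, the section still needs correcting. A hazard ratio of 1.93 comes close only at 95% power (121 events), which is not the stated power, and no time-to-event analysis is planned.

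A second reply is that 122 may be a chosen number with power of at least 0.99, not the calculated minimum. That is possible, but the section presents inputs and a result and mentions no choice above the minimum.

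Third, the sensitivity figures are not a two-sided bound. Durations may be skewed, and Mann-Whitney can then be more efficient than the t-test. In simulations with 61 per group and a pure shift of 0.524 SD, power was about 97% for lognormal data (log-SD 0.6) and 98% for exponential data, against 80% for normal data. This stands. The shapes are assumed, and the figures above should be read as a normal-data case and a conservative floor.

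Finally, the number errs on the safe side and the text describes the trial as already conducted, so no design decision depends on it. That limits the seriousness but does not make the stated figure right.

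**Conclusion.** The concern holds. With 1.93 as Cohen's d and a two-sided alpha of 0.05, the stated inputs need 22 to 26 women in total, not 122. No choice of test or sidedness, and no plausible loss rate, closes the gap. The one reading that would reconcile the figures needs an SD that the documents do not give.

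The consequence is for reporting, not validity. With all 61 per group analysed, the difference detectable at 99% power is 0.80 to 0.84, or 41 to 44% of 1.93. It rises if exclusions after allocation reduce the analysed number: at an assumed 20% loss the upper figure is 0.94, or 49% of 1.93. These figures assume the groups differ by a pure shift; skewed data could give more power. Which of the stated figures is wrong cannot be settled from the documents. The point should be fixed, but it does not threaten the trial's conclusions.

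**What to change.** Keep 122. In section 7, remove the claim that an effect size of 1.93 at 99% power yields it. State what was actually used: the effect-size metric, the means and SDs taken from the cited study, the test, the sidedness and any inflation. Give a reason for the larger number only if it was the real one at the time.

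Add a sensitivity statement that is plainly marked as retrospective, for example:

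> Added retrospectively, not the basis of the planned size: if all 61 per group are analysed (two-sided alpha 0.05, Mann-Whitney), the detectable standardised difference is about 0.52 at 80% power, 0.61 at 90% and 0.80 at 99% with normal data, and about 0.55, 0.64 and 0.84 at the minimum efficiency of 0.864. It is larger if exclusions after allocation reduce the analysed number. These figures assume a pure shift between groups; skewed data could give higher power.

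The cost is wording only, with no change to enrolment or analysis. The sponsor must retrieve the original G*Power inputs and accept a less impressive statement of what the trial can detect.

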## 8. Interventions

**Intervention Group:** Participants were informed and consented. A perineal mirror was fixed to the delivery bed during the second stage of labor, allowing women to visualize fetal descent.

**Control Group:** Received standard care with no mirror.

### **Outcome Measures**

#### **Primary Outcome:**

Duration of second stage of labor (in minutes)

#### **Secondary Outcome:**

Maternal childbirth experience using the Childbirth Experience Questionnaire (CEQ)

## 10. Data Collection Tools

Personal Information Form

CEQ (validated Turkish version)

Opinion Form on Labor Mirror Use

## **11. Statistical Analysis Plan**

Descriptive statistics (mean, SD, frequencies)

Shapiro-Wilk test for normality

Mann-Whitney U test for group comparisons

Pearson Chi-Square for categorical variables

p-value <0.05 considered statistically significant

Software: IBM SPSS Statistics v20

## **12. Ethical Considerations**

**Approval:** Kocaeli Derince Training and Research Hospital Ethics Committee (2023-13)

Written informed consent obtained

Data anonymized

Compliance with Declaration of Helsinki

## **13. Data Sharing Statement**

Data is available from the corresponding author upon reasonable request.

